5.6.3. Additional Safety Assessments

5.6.3.1. Clinical Laboratory Tests

Descriptive statistics of chemistry, hematology, and urinalysis (pH and specific gravity) laboratory tests and changes from baseline will be presented at each scheduled time point by intervention group.

Abnormality criteria based on normal ranges will be applied to baseline and postbaseline values. Shift tables will be provided summarizing the shift in laboratory values from baseline to scheduled time points with respect to abnormality criteria (low, normal, high). A listing of participants with any laboratory results outside of the reference ranges will be provided.

A listing of participants meeting any of the following hepatic toxicity stopping criteria (confirmed by repeat testing) will be provided:

• Aspartate aminotransferase (AST) exceeds 5x the upper limit of normal (ULN)

- Alanine aminotransferase (ALT) exceeds 5x the ULN
- AST exceeds 3x the ULN and total bilirubin exceeds 1.5x ULN
- ALT exceeds 3x the ULN and total bilirubin exceeds 1.5x ULN

The number and percentage of participants with positive urine drug screen results will be presented over time by intervention group.

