1.3. Schedule of Activities (SoA)

Phase	Screening	Double-blind treatment phase							Follow-up or EW^h (7 to 14 days after last study visit)
		1	2	3	4	5	6	7	
Visit number ^a	1								
Week (end of)	-4 to 0	0	1	2	3	4	5	6	7/8
Study Day	-28 to -1	1	8	15	22	29	36	43	49-56
Visit window			± 1 day	± 1 day	± 1 day	± 1 day	± 1 day	± 1 day	
Clinic Visit	C	C	C	C	C	C	C	C	
Screening/Administrative									
Informed consent ^b	X								
MINI interview with Borderline Personality Disorder module	X								
ATHF-SF	X								
Inclusion/exclusion criteria	X	X ^{n ad}							
Prestudy therapies	X								
Medical history and demographics	X								
Download and install/register Digital Health Assessment app ^{q,r,c}	X	X							
Safety Assessments									
Physical examination	X	X						X	X
Height	X								
Body weight	X	X						X	X
Urine Drug Screen ^{ab}	X ^m	X	X	X		X		X	X
Alcohol Breath Test	X	X						X	
Pregnancy test ^d	X	X	X	X		X		X	X
Vital signs (supine blood pressure, heart rate, tympanic or oral temperature, respiratory rate)	X	X ⁿ	X ^e	X ^e		X ^e		X ^e	X
12-lead ECG ^g	X	X ⁿ	X ^e	X ^e		X ^e		X ^e	X
YMRS	X	X ^w	X ^u	X ^u		X ^u		X ^u	
C-SSRS ^f	X	X ^w	X ^u	X ^u		X ^u		X ^u	X
Study Intervention Administration									
Randomization		X							
Dispense study intervention		X		X		X			
Oral dose study intervention ^{i,j}		Day 1 up to and including Day 43 ⁱ ± 1 day							
Study intervention accountability by the site		X		X		X		X	

Phase	Screening	Double-blind treatment phase							Follow-up or EW^h (7 to 14 days after last study visit)
		1	2	3	4	5	6	7	
Visit number^a		1	2	3	4	5	6	7	
Week (end of)	-4 to 0	0	1	2	3	4	5	6	7/8
Study Day	-28 to -1	1	8	15	22	29	36	43	49-56
Visit window			1 day	1 day	1 day	1 day	1 day	1 day	
Clinic Visit	C	C	C	C		C		C	
Blood and Urine Collection^m									
Clinical Laboratory tests: Hematology, serum chemistry and urinalysis	X	X		X		X		X	X
Serology, HbA1c	X ^{ac}								
Blood sample collection for PK JNJ-55308942		X ^l	X ^l	X ^l		X ^l		X ^l	
Blood samples for other biomarkers ^k		X		X		X		X	
Blood for research samples (TruCulture) ^x		X						X	
Blood for research sample (PBMCs) ^y		X							
Blood samples for hormones (males only) ^v		X				X		X	X
Blood sample for Pharmacogenomics (general SNPs) ^{aa}		X							
Blood sample for GoF and LoF SNPs (P2X7)	X								
Blood sample for RNA		X ^k				X ^k		X ^k	
Clinician-Administered Assessments									
Structured Interview Guide for HDRS ₁₇ (SIGH-D)	X	X ^p							

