2.3.1. Risks for Study Participation

Potential Risks of Clinical Significance	Summary of Data/ Rationale for Risk	Mitigation Strategy
Emerging safety and tolerability profile in human participants	JNJ-55308942 has not been dosed in humans for >10 days and patients with bipolar depression have not previously been exposed to JNJ-55308942.	Participants in this study will have to attend scheduled visits to the study site, where the safety and tolerability of the study intervention will be evaluated along with efficacy evaluations. Patients will be regularly evaluated for symptom changes.

Risks Due to Study Intervention(s) [JNJ-55308942]

Testicular toxicity (males only)	[C] [C] toxicity was seen in the 1-, 3-, and 6-month toxicity studies in Sprague Dawley rats with JNJ-55308942. No [C] [C] toxicity was observed in similar studies in dogs with up to 9 months of dosing.	Male participants in this study will have regular [C] [C] measurements at defined timepoints. The dose of [C] mg once-daily has a predicted >12-fold safety margin.
----------------------------------	--	--

Drug-Drug Interactions	
JNJ-55308942 is a weak inducer of CYPCCI and a moderate inhibitor of CYPCCI
 
JNJ-55308942 is mainly metabolized by CYPCCI.
	
The use of concomitant medications that are metabolized solely by CYPCCI should preferably be avoided, or participants should be carefully monitored.
 
Co-administration with moderate or strong inhibitors/inducers of CYPCC should be avoided.
 
A list of disallowed concomitant therapies is provided in Section 10.6

------------------------	--	---

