Assessment of Disease Progression at Home***Self-Assessment of Well-Being (SAWB)***

The SAWB questionnaire is a multiple-item self-report questionnaire designed to provide additional information regarding the participant's subjective experience while taking study intervention. This is an internal Janssen questionnaire, and the questions will be asked to the participant daily by the Digital Health Assessment app during the double-blind treatment phase. Several items of interest can be covered: such as, but not limited to, the pattern of sleep, energy level, and concentration level.

Safety Assessments

Standard safety assessments including physical examination, body weight, vital signs (including oral, tympanic or temporal body temperature, pulse/heart rate, and respiratory rate), 12-lead ECG, urine drug testing, alcohol breath test, pregnancy testing (female participants only), and clinical labs (hematology, chemistry panel, hormones [male participants only], and urinalysis) will be performed as per SoA. In addition, serology and hemoglobin A1C (HbA1C) assessments will be performed at screening only.

Additionally, emergence of suicidal ideation will be assessed using the C-SSRS at screening and during each visit.

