8.6.4. Clinical Safety Laboratory Assessments

Blood samples for serum chemistry, hematology, hormone levels (if applicable), and pregnancy testing (if applicable) and urine samples for urinalysis and pregnancy testing (if applicable) will be collected as noted in Appendix 2: Clinical Laboratory Tests. The investigator must review the laboratory results, document this review, and record any clinically relevant changes occurring during the study in the AE section of the electronic case report form (eCRF). In addition, serology

and HbA1C assessments will be performed at screening only. The laboratory reports must be filed with the source documents.

A urine drug screen (UDS) and an alcohol breath test will be performed at the timepoints indicated in the SoA.

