9.4.3. Safety Analyses

All safety analyses will be performed on the Safety population.

Statistical analysis of the safety data will be done by the sponsor or under the authority of the sponsor. Specific details will be provided in the SAP.

Safety summaries will be provided by treatment, unless specified otherwise.

AEs will be coded using the current version of Medical Dictionary for Regulatory Activities (MedDRA) and tabulated by system organ class, by severity and relationship to study intervention and will be presented by intervention. SAEs will be summarized separately.

The safety analysis will include the incidence of AEs, actual data and changes in blood pressure, pulse/heart rate, oral, tympanic, or temporal body temperature, laboratory safety data, 12-lead ECG, and physical examination data from Day 1 predose to all postdose assessments.

Results from the C-SSRS will be tabulated by treatment group for all participants receiving at least 1 dose of study intervention.

Exploratory analyses for changes in YMRS total score, as well as for individual YMRS items, from baseline will be performed. Details will be provided in the SAP.

Adverse Events

The verbatim terms used in the CRF by investigators to identify adverse events will be coded using the Medical Dictionary for Regulatory Activities (MedDRA). Any AE occurring at or after the initial administration of study intervention through the day of last dose plus 30 days is considered to be treatment emergent. All reported treatment-emergent AEs will be included in the analysis. For each AE, the percentage of participants who experience at least 1 occurrence of the given event will be summarized by study intervention group. In addition, comparisons between study intervention groups will be provided, if appropriate.

Summaries, listings, datasets, or participant narratives may be provided, as appropriate, for those participants who die, who discontinue study intervention due to an AE, or who experience a severe or a serious AE.

Clinical Laboratory Tests

Laboratory data will be summarized by type of laboratory test. Reference ranges will be used in the summary of laboratory data. Descriptive statistics will be calculated for each laboratory analyte at baseline (Day 1 predose) and at each scheduled time point. Changes from baseline results will be presented in pre- versus post-treatment cross-tabulations (with classes for below, within, and above normal ranges).

Electrocardiogram

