10.2. Appendix 2: Clinical Laboratory Tests

The following tests will be performed according to the Schedule of Activities by the central laboratory.

Protocol-Required Safety Laboratory Assessments

Laboratory Assessments	Parameters		
Hematology	Platelet count Red blood cell count Hemoglobin Hematocrit	RBC Indices: MCV MCH % Reticulocytes	White Blood Cell (WBC) count with Differential: Neutrophils Lymphocytes Monocytes Eosinophils Basophils
Clinical Chemistry	Sodium Potassium Chloride Bicarbonate Blood urea nitrogen (BUN) Creatinine Glucose Aspartate aminotransferase (AST)/Serum glutamic-oxaloacetic Alanine aminotransferase (ALT)/Serum glutamic-oxaloacetic Gamma-glutamyltransferase (GGT)	Total bilirubin (Tbili) and Direct bilirubin Alkaline phosphatase Creatine phosphokinase (CPK) Lactic acid dehydrogenase (LDH) Uric acid Calcium Phosphate Albumin Total protein Cholesterol Triglycerides Magnesium	
Routine Urinalysis	Dipstick Specific gravity pH Glucose Protein Blood Ketones Bilirubin Urobilinogen Nitrite Leukocyte esterase	Sediment (if dipstick result is abnormal) Red blood cells White blood cells Epithelial cells Crystals Casts Bacteria	If dipstick result is abnormal, flow cytometry or microscopy will be used to measure sediment.
Hormones	Women only: Follicle Stimulating Hormone (FSH) (at screening) Males only: Inhibin B Luteinizing hormone (LH) Prolactin Total Testosterone (low sensitivity = LC/MS-MS) Total Testosterone (high sensitivity = ELISA) Free Testosterone		

	Sex Hormone Binding Globulin (SHBG)
Other Screening Tests	
• Serum β-hCG pregnancy test performed at Screening (WOCBP only). At all other time points, if the urine pregnancy test is positive, a serum β-hCG test will be performed. Investigators may perform additional serum or urine pregnancy testing at their discretion as clinically needed.• Serology (human immunodeficiency virus [HIV] antibody, hepatitis B surface antigen [HBsAg], and hepatitis C virus [HCV] antibody)• HbA1c at screening• Urine drug screen (UDS) (opiates [including methadone], cocaine, barbiturates, cannabinoids, and amphetamine/methamphetamine). At screening: a urine sample will be analysed by the central lab. At all other visits: a dipstick test will be used and only in case of a positive result will the urine sample be analysed by the central lab for confirmation of the positive result.• Alcohol breath test

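### SAP 5.6.3.1 guarantees no by-arm change from baseline for the male hormone panel, although the protocol classes the panel as safety laboratory tests and promises a summary of every analyte

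*SAP*

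**What the plan says.** **Protocol.** The risk table in section 2.3.1 has a row headed "Testicular toxicity (males only)". Its mitigation column begins "Male participants in this study will have regular", and the measurement itself is blacked out. The Schedule of Activities (1.3) has a separate line, "Blood samples for hormones (males only)", marked at Day 1, Day 29, Day 43 and follow-up or early withdrawal. Section 4.2 places the panel inside the safety laboratory tests: "clinical labs (hematology, chemistry panel, hormones [male participants only], and urinalysis) will be performed as per SoA". Section 8.6.4 does the same, beginning "Blood samples for serum chemistry, hematology, hormone levels (if applicable), and pregnancy testing". Appendix 2, under the protocol-required safety laboratory assessments, lists inhibin B, LH, prolactin, total testosterone by two assays (one being "Total Testosterone (low sensitivity = LC/MS-MS)"), free testosterone and SHBG for men. For the analysis, section 9.4.3 says "Descriptive statistics will be calculated for each laboratory analyte at baseline (Day 1 predose) and at each scheduled time point". It makes safety summaries by treatment the default and leaves the details to the SAP.

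**SAP.** Section 5.6.3.1 opens with "Descriptive statistics of chemistry, hematology, and urinalysis (pH and specific gravity) laboratory tests" and their changes from baseline, at each scheduled time and by intervention group. It then provides low/normal/high shift tables for laboratory values, a listing of participants with out-of-range results, a listing for the hepatic criteria, and urine drug screen counts. The laboratory row of Table 2 covers hematology, serum and urinalysis. SAP Appendix 2, which records changes to protocol-planned analyses, has two entries: the mRNA subgroup, and the Day 1 assessments done after dosing.

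**The concern.** The SAP determines what appears in the study report. It gives by-arm descriptive statistics and change from baseline to three laboratory classes, and male hormones are not one of them. No SAP section names testosterone, inhibin B, LH, prolactin or SHBG.

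Testicular toxicity is the only organ toxicity named in the protocol's risk table. The same table says that the drug has not been given to humans for more than 10 days, so a 6-week trial is the first longer exposure in men. Section 4.3 supports including men by a 12-fold exposure margin to the rat no-effect level. A by-arm summary of reproductive hormones is the direct human check on that reasoning. If the SAP is followed to the letter, the report could omit it although the blood has been drawn.

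**Working it through.** The plan gives no figure on this point, so the check is mainly a comparison of texts.

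1. **Is the panel a safety laboratory test?** Protocol 4.2, 8.6.4 and Appendix 2 say yes. The safety endpoint (protocol section 3, SAP 1.1) names only chemistry, hematology and urinalysis. The synopsis safety evaluations and the Schedule of Activities list hormones apart from those three. The protocol is therefore not uniform, but Appendix 2 is explicit.

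2. **What analysis does the protocol promise?** Section 9.4.3 covers each analyte at baseline and at each scheduled time, with pre/post cross-tabulations and summaries by treatment. It does not exclude hormones.

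3. **What does the SAP specify for hormones?**
   - *Descriptive statistics and change from baseline by arm:* not specified, because the sentence names three classes.
   - *Shift tables:* general wording that could include hormones. The sentence does not name the intervention group.
   - *Out-of-range listing:* general wording that could include hormones. A listing does not compare arms.
   - *Visit windows:* no hormone row. The existing laboratory row includes a Week 2 window (days 2 to 21), when no hormone sample is scheduled.
   - *Declared change in SAP Appendix 2:* none.

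4. **Is there another route?** SAP 1.1 names hormonal markers only within an exploratory biomarker endpoint. SAP section 1 sends other biomarker analyses to separate documents, if they are done at all.

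5. **Extent.** Inhibin B, LH, prolactin, total testosterone (two assays), free testosterone and SHBG make 1 + 1 + 1 + 2 + 1 + 1 = 7 results. There are three post-baseline times (Day 29, Day 43, follow-up), so 7 × 3 = 21 change-from-baseline summaries per arm are not specified.

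6. **Would a by-arm summary be informative?** The documents do not give the share of men, so assume 30% to 60%, equal in both arms. Sex is not a stratification factor, so equality is only approximate. With 82 randomised per arm, 0.30 × 82 ≈ 25 and 0.60 × 82 ≈ 49 men per arm. The half-width of a 95% interval for an arm difference, in SD units, is 1.96 × √(2/m):
   - m = 25: 1.96 × √(2/25) = 0.55 SD
   - m = 49: 1.96 × √(2/49) = 0.40 SD

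   With 132/2 = 66 completers per arm, m runs from about 20 to 40 and the half-width from 0.62 down to 0.44 SD. At the 80% level used elsewhere in the SAP, the multiplier 1.2816 gives 0.36 to 0.26 SD for those randomised. The summary is feasible and would show a large shift, but it is imprecise for a small one.

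**The case against.** The strongest reply is that the SAP follows the protocol's own endpoint wording, which limits clinical laboratory tests to the same three classes, and that the Schedule of Activities keeps hormones on a separate line. On that reading nothing was narrowed. The observation is fair and shows that the protocol needs reconciling. It does not remove the explicit listing in Appendix 2 or the commitment in 9.4.3 to each analyte.

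The remaining SAP outputs also count. A reader might infer that hormones will get no table, shift or listing, or will never be compared. The documents do not support that: the shift tables and the out-of-range listing are worded generally enough to include hormones, and a biomarker document could cover them. What stands is narrower. Neither route guarantees a by-arm change from baseline, and a mean fall that stays within the reference range would show in neither the shift tables nor the listing.

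Individual safety does not depend on the missing summary. Under 8.6.4 investigators review results and record clinically relevant changes as adverse events. Under 7.3 the sponsor monitors laboratory data while blinded. SAP 5.6.2 tabulates treatment-emergent events by arm.

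A reader might also take the rat finding as irreversible. Protocol 2.2 (organ names blacked out) reports no reversal after a 3-month recovery period in the longer studies, but full recovery after 1 month in the 1-month study. Six weeks of dosing lies between those durations. Section 2.3.1 adds that dogs dosed for up to 9 months showed no such toxicity.

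**Conclusion.** The point holds as a gap between protocol 9.4.3 and SAP 5.6.3.1. For the male hormone panel the SAP specifies no by-arm descriptive statistics or change from baseline, assigns no visit window, and does not declare the difference. The extent is seven assay results at three post-baseline times. The primary analysis and the sample size are unaffected.

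Two assumptions carry the conclusion. First, Appendix 2 and section 4.2 are taken as the protocol's classification of hormones, ahead of the shorter endpoint wording. Second, the hormone panel is taken to be the measurement that mitigates the testicular risk. That is a strong inference from a scheduled, males-only panel of reproductive hormones, but the risk-table entry is blacked out and does not state it. The precision figures also rest on an assumed share of men.

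The gap should be closed, because doing so costs almost nothing and the panel addresses a named risk. It is not evidence that the data will go unused or that participants are unmonitored.

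**What to change.** In SAP 5.6.3.1, add the male hormone panel for men in the safety set: inhibin B, LH, prolactin, total testosterone (each assay separately), free testosterone and SHBG. Specify descriptive statistics, change from baseline and reference-range shift tables by intervention group at Day 29, Day 43 and follow-up. State that the out-of-range listing includes these analytes. Add a hormone row to Table 2 with targets Day 1, Day 29, Day 43 and follow-up. If the sponsor intends to leave the panel out of the study report, SAP Appendix 2 should say so, give the reason and state where it will be reported.

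A baseline-adjusted arm difference with a confidence interval would be useful for inhibin B, LH and testosterone. It is optional, since the protocol promises only descriptive statistics and cross-tabulations for laboratory data.

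The cost is a short SAP revision and a few tables. The samples are already scheduled, so no protocol amendment, extra blood or additional participants are needed.

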5.6.3.2. Vital Signs and Physical Examination Findings

Vital sign parameters that will be analyzed are temperature (oral, tympanic, or temporal), respiration rate, pulse, blood pressure (systolic and diastolic), weight, and Body Mass Index (BMI). BMI will be calculated as weight (kg)/(height (m))². The height measurement collected at screening will be used in the calculation. Change from baseline will be summarized at each assessment time point by intervention group.

Vital sign parameters and changes from baseline will be summarized using descriptive statistics at each scheduled time point by intervention group.

Abnormality criteria (as defined in Table 4) will be applied to baseline and postbaseline values. For baseline values, increase or decrease criteria are not applied.

Postbaseline values will be considered treatment-emergent if they meet both value and change criteria in Table 4.

For criteria that do not include an increase or decrease from baseline:

- Treatment-emergent will be concluded if the postbaseline value is above the upper limit and the baseline value is below the upper limit (e.g., Normal or Low). The same applies to the postbaseline value being below the lower limit with the baseline value being above the lower limit (e.g., Normal or High).
- If the baseline value is missing, a postbaseline abnormality will always be considered as treatment-emergent.

Incidence of treatment-emergent clinically important abnormalities in vital signs during intervention will be summarized at each scheduled time point by intervention group. A listing of participants with clinically important abnormalities in vital signs will be presented.

Table 4: Clinically Important Abnormalities in Vital Signs

Vital Sign	Abnormal Category	Criteria	
Pulse	Abnormally high	>100 bpm and with >15 bpm increase from baseline	
	Abnormally low	<50 bpm and with >15 bpm decrease from baseline	
Systolic blood pressure	Abnormally high	>180 mm Hg and with >20 mm Hg increase from baseline	
	Abnormally low	<90 mm Hg and with >20 mm Hg decrease from baseline	

Vital Sign	Abnormal Category	Criteria	
Diastolic blood pressure	Abnormally high	>105 mm Hg and with >15 mm Hg increase from baseline	
pressure	A har a mare aller 1 arry	250 mm Ha and with >15 mm Ha decrease from heading	
	Abnormally low	<50 mm Hg and with >15 mm Hg decrease from baseline	
Temperature	Abnormally high	>37.5°C	
	Abnormally low	<35.5°C	
Weight	Abnormally high	increase >7% from baseline	
	Abnormally low	decrease >7% from baseline	
Respiratory rate	Abnormally high	>20 breaths per minute	

In addition, a by-subject listing of the abnormal physical examination data will be presented.

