Descriptive statistics of body temperature, pulse/heart rate, supine blood pressure, and respiratory rate values and changes from baseline will be summarized at each scheduled time point. The percentage of participants with values outside clinically relevant limits will be summarized.

Physical Examination

Abnormalities observed during the physical examination will be summarized and listed by treatment group at each scheduled time point.

Young Mania Rating Scale (YMRS)

Exploratory analyses will be performed for changes from baseline in YMRS total score and for changes from baseline in individual YMRS items by treatment group for all participants receiving at least 1 dose of study intervention. Details will be provided in the SAP.

Columbia Suicide Severity Rating Scale (C-SSRS)

Results from the C-SSRS will be tabulated by treatment group for all participants receiving at least 1 dose of study intervention.

[figure not shown]
Interim analysis

No interim analysis is planned.

It may be recommended that an unblinded data review needs to be performed by an independent reviewer (e.g., data review committee) if deemed critical by the Janssen clinical team. Committee membership responsibilities, authorities, and procedures will be documented in a charter.

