Electrocardiogram data will be summarized by ECG parameter. Descriptive statistics will be calculated at baseline and for observed values and changes from baseline at each scheduled time point. Frequency tabulations of the abnormalities will be made.

The ECG variables that will be analyzed are pulse/heart rate, PR interval, QRS interval, QT interval, and corrected QT (QTc) interval using [some or all of] the following correction methods: QT corrected according to Bazett's formula (QTcB) and QT corrected according to Fridericia's formula (QTcF).

Descriptive statistics of QTc intervals and changes from baseline will be summarized at each scheduled time point. The percentage of participants with QTc interval >450 msec (males), >470 (females), >480 msec, or >500 msec will be summarized, as will the percentage of participants with QTc interval increases from baseline >30 msec or >60 msec. Also, descriptive statistics of QTc will be provided by gender.

Vital Signs

Descriptive statistics of body temperature, pulse/heart rate, supine blood pressure values and changes from baseline will be summarized at each scheduled time point. The percentage of participants with values beyond clinically important limits will be summarized.

Physical Examinations

Abnormalities observed during the physical examination will be summarized and listed by treatment group at each scheduled time point.

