5.6.3.3. Electrocardiogram

The ECG parameters that will be analyzed are heart rate (HR), PR interval, QRS interval, QT interval, and corrected QT(QTc) interval using the following correction methods: Bazett's formula (QTcB), and Fridericia's formula (QTcF).

Bazett's formula: QTcB (msec) = QT (msec) * $(HR(bpm)/60)^{0.5}$;

Fridericia's formula: QTcF (msec) = QT (msec) * $(HR(bpm)/60)^{0.33}$

If ECG measurements are repeated at a visit, they will be averaged. The averaged value will considered the 'Visit' ECG result.

Descriptive statistics of ECG parameters and change from baseline will be summarized at each scheduled time point by intervention group.

The number and percentage of participants with categorized QTc interval values will be summarized at each scheduled time point. The number and percentage of participants with categorized QTc interval increases from baseline to the maximum postbaseline value will be summarized. A shift table will be provided summarizing the shift from baseline to maximum QTc interval classification. Refer to Table 5 for summary categories.

Table 5: Criteria for Abnormal QTc Values and Changes from Baseline

QTc value (msec)	Normal QTc	nal QTc ≤450 for male, ≤470 for female	
		>450 to ≤480 for male, >470 to ≤480 for female	
		>480 to \(\leq 500\)	
		>500	
QTc change from baseline (msec)	No concern	≤30	
	Concern	>30 to ≤60	
	Clear concern	>60	

Abnormality criteria (Table 6) will be applied to baseline and postbaseline values. Postbaseline abnormalities will be compared with their corresponding baseline result:

- Treatment-emergent will be concluded if the postbaseline value is above the upper limit and the baseline value is below the upper limit (e.g., Normal or Low). The same applies to the postbaseline value being below the lower limit with the baseline value being above the lower limit (e.g., Normal or High).
- If the baseline value is missing, a postbaseline abnormality will always be considered as treatment-emergent.

The number and percentage of participants with treatment-emergent abnormal postbaseline values (relative to baseline) will be presented by intervention group over time:

ECG Parameter	Abnormally low	Abnormally high
Heart Rate (bpm)	<50 bpm	>100 bpm
PR interval (msec)	<120 msec	>200 msec
QRS interval (msec)	<60 msec	>120 msec
QT interval (msec)	<200 msec	>500 msec

Table 6: Abnormal Limits for ECG Parameters

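### Vital-sign abnormalities and heart rate, PR, QRS and QT abnormalities are tabulated by visit only, so no planned table shows by arm how many participants were ever affected on treatment

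*SAP*

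**What the plan says.** SAP 5.6.3.2 sets clinically important vital-sign limits in Table 4 and then plans the summary: "Incidence of treatment-emergent clinically important abnormalities in vital signs during intervention will be summarized at each scheduled time point by intervention group". It adds: "A listing of participants with clinically important abnormalities in vital signs will be presented". SAP 5.6.3.3 does much the same for heart rate, PR, QRS and QT against the limits in Table 6: "The number and percentage of participants with treatment-emergent abnormal postbaseline values (relative to baseline) will be presented by intervention group over time".

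QTc is handled differently in that section. In addition to by-visit categories, the SAP says: "The number and percentage of participants with categorized QTc interval increases from baseline to the maximum postbaseline value will be summarized". It also says: "A shift table will be provided summarizing the shift from baseline to maximum QTc interval classification". SAP 5.6.3.4.2 likewise takes each participant's C-SSRS result to its maximum postbaseline score.

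For vital signs, Protocol 9.4.3 plans descriptive statistics at each scheduled time point. A separate sentence, with no time frame, then says: "The percentage of participants with values beyond clinically important limits will be summarized". The synopsis (Protocol 1.1) is parallel: "The percentage of participants with values outside clinically relevant limits will be summarized". For ECG measures other than QTc, the protocol plans only frequency tabulations. SAP Appendix 2, which records changes to protocol-planned analyses, has no entry on this point.

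SAP 5.1.2 keeps one visit per analysis window: the one closest to the target day, or the later one on a tie. Any other visit in the window is left out of summaries and analyses.

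**The concern.** By-visit rows answer how many participants were abnormal at a given visit. They do not answer how many were abnormal at any time on treatment, because the same person may appear in several rows. The rows therefore cannot be added up. The wording of SAP 5.6.3.2 refers to incidence during intervention, yet no row gives it.

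What is at stake is a participant-level, between-arm safety comparison. An effect that appears in different participants at different visits looks small in every row. The visit-window rule adds to this: an abnormal value at an extra visit, possibly one arranged because of a safety concern, can drop out of the tables altogether.

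The parameters are of some interest here. Protocol 2.2 describes the nonclinical cardiovascular effects as hemodynamic. Protocol 2.3.1 notes that humans had not been dosed for more than 10 days and that patients with bipolar depression had not been exposed. The SAP gives no reason for using worst-value summaries for QTc and the C-SSRS but not for pulse, blood pressure, heart rate, PR and QRS.

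**Working it through.** **Inputs**
- Participants per arm: 82 (SAP 3; Protocol 9.2).
- On-treatment postbaseline visits for vital signs and ECG: Weeks 1, 2, 4 and 6 (SAP Table 2), so k = 4.
- By-visit abnormality share p: the documents give none, so every value of p below is an assumption.

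**The plan's own figure.** The 82 per arm reproduces. With effect size 0.45, 1-sided alpha 0.10 and 90% power, n = 2 × (1.2816 + 1.2816)² / 0.45² = 64.9, or 65 per arm. Dividing by 0.80 for 20% dropout gives 81.25, or 82. The figure is not in dispute and serves here only as a denominator.

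**Bounds on the share ever affected.** With the same participants assessed at every visit, the share ever affected is at least the largest by-visit share (the same people each time). It is at most the sum of the by-visit shares (different people each time). With an equal share p at each of four visits, this runs from p to 4p. If visits are independent it is 1 − (1 − p)⁴.

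| Assumed p | Count per visit (82p) | Ever: same people | Ever: independent visits | Ever: different people |
|---|---|---|---|---|
| 1% | 0.8 | 1% (0.8) | 3.9% (3.2) | 4% (3.3) |
| 2% | 1.6 | 2% (1.6) | 7.8% (6.4) | 8% (6.6) |
| 4% | 3.3 | 4% (3.3) | 15.1% (12.4) | 16% (13.1) |
| 5% | 4.1 | 5% (4.1) | 18.5% (15.2) | 20% (16.4) |

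Numbers of participants out of 82 are in parentheses.

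**Two arms.** Suppose the rows show 2% in one arm and 4% in the other at every visit. The ever-affected shares could then be anywhere in 2–8% and 4–16%. These ranges overlap, so by-visit rows alone do not fix even the direction of the difference in participants affected.

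**Limits of the arithmetic**
- It treats all 82 as assessed at each visit. With 20% dropout, about 82 × 0.80 = 65.6 per arm would remain at Week 6.
- Abnormal values at extra visits dropped under SAP 5.1.2 would come on top of the upper bound.
- It does not apply to weight. The schedule of activities has one on-treatment postbaseline weight (Day 43), so the Week 6 row is already close to the on-treatment total.
- It does not apply to QTc, which is summarized to the maximum postbaseline value.

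**The case against.** **The protocol does not ask for an any-time percentage.** A reader might infer that the SAP fails to deliver what the protocol promised. The documents do not establish this. Neither vital-sign sentence in the protocol states a time frame, and Protocol 9.4 leaves technical detail to the SAP. An any-time reading is the more natural one, because the time-point qualifier in the preceding sentence is not repeated, but a by-visit reading is permissible. For ECG measures other than QTc, Table 6 does supply the planned frequency tabulation. This objection stands.

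**ECG is not counted only by visit.** A reader might extend the point to ECG as a whole. That would be wrong: QTc, the one ECG measure for which the protocol names percentages of participants, has both an increase summary and a shift table on the maximum value. The ECG gap is confined to Table 6.

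**Other outputs carry the safety comparison.** Descriptive statistics of values and changes are planned by arm for every parameter, so it would be wrong to say that the comparison rests on small by-visit counts alone. The vital-sign listing allows a hand count. Clinically relevant changes are to be recorded as adverse events (Protocol 8.6 and 8.6.3), and SAP 5.6.2 counts participants with at least one occurrence. All this is true, but mean changes can hide a few extreme values, a listing is not a comparison by arm, and adverse events depend on investigator judgment and not on the Table 4 or Table 6 limits.

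**The harm is speculative.** On-treatment vital signs and ECGs are taken predose, so a short-lived postdose effect would be missed under either tabulation. Protocol 2.2 reports no consistent treatment-related vital-sign or ECG effects in the clinical studies. The nonclinical exposures are redacted, so their relevance cannot be judged. These points limit the importance of the gap but do not close it.

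**Conclusion.** The point holds as a low-cost improvement to safety reporting. For the Table 4 vital signs other than weight, and for heart rate, PR, QRS and QT in Table 6, no planned table gives the number of participants in each arm with at least one treatment-emergent abnormality on treatment.

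That this number cannot be recovered from the by-visit rows does not depend on any assumed rate. The factor of 1 to 4 assumes equal by-visit shares and full attendance at four visits. Specific counts, such as about 6 versus 12 participants ever affected at 2% versus 4% per visit, also need independent visits and are illustrations; a reader should not take them as an expected effect. The primary analysis and the sample size are not affected.

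**What to change.** Add one row per abnormality criterion to the Table 4 and Table 6 summaries: the number and percentage of safety-set participants, by arm, with at least one treatment-emergent abnormality at any on-treatment postbaseline assessment. The by-visit rows stay.

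The SAP should state three things with it:
- extra and unscheduled assessments count toward this row, even where the visit-window rule in SAP 5.1.2 excludes them from the by-visit rows;
- the end of the on-treatment period, because follow-up and early-withdrawal visits share one label in SAP Table 2;
- the denominator, because neither SAP section gives one for these tables.

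The row uses data already collected and the existing abnormality rules. The cost is minor extra programming, and no planned output is lost.
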